**Study Day 57 ( $\pm 0$  days; 1 day after Vaccination #3)**

1. Perform basic history and focused physical examination (including injection site), emphasizing examination of any acute complaints.
2. Record vital signs (blood pressure, temperature, and heart rate).
3. Record AEs and concomitant medications, if applicable.

**Study Day 59 ( $\pm 1$  day; 3 days after Vaccination #3)**

1. Perform basic history and focused physical examination (including injection site), emphasizing examination of any acute complaints.
2. Record vital signs (blood pressure, temperature, and heart rate).
3. Record AEs and concomitant medications, if applicable.
4. Obtain approximately 6.0 mL of blood for CBC with differential and platelet count, ALT, creatinine, and transcriptional analysis.

**Study Day 63 ( $\pm 2$  days; 7 days after Vaccination #3)**

1. Perform basic history and focused physical examination (including injection site), emphasizing examination of any acute complaints.
2. Record vital signs (blood pressure, temperature, and heart rate).
3. Record AEs and concomitant medications, if applicable.
4. Obtain approximately 5.0 mL of blood for anti-Pfs230 antibody ELISA, and standard membrane feeding assay (SMFA).

**Study Day 70 ( $\pm 7$  days; 14 days after Vaccination #3)**

1. Perform basic history and focused physical examination, emphasizing examination of any acute complaints.
2. Record vital signs (blood pressure, temperature, and heart rate).
3. Record AEs and concomitant medications, if applicable.
4. Obtain approximately 17.5 mL of blood for CBC with differential and platelet count, ALT, creatinine, malaria blood smear, malaria PCR, anti-Pfs230 antibody ELISA, standard membrane feeding assay (SMFA) and transcriptional analysis.

**Study Day 84 ( $\pm 7$  days; 28 days after Vaccination #3)**

1. Perform basic history and focused physical examination, emphasizing examination of any acute complaints.
2. Record vital signs (blood pressure, temperature, and heart rate).
3. Record AEs and concomitant medications, if applicable.

**Study Day 112 ( $\pm 7$  days; 56 days after Vaccination #3)**

1. Perform basic history and focused physical examination, emphasizing examination of any acute complaints.
2. Record vital signs (blood pressure, temperature, and heart rate).
3. Record AEs and concomitant medications, if applicable.
4. Obtain approximately 6.5 mL of blood for malaria blood smear, malaria PCR, anti-Pfs230 antibody ELISA, standard membrane feeding assay (SMFA).

**Study Day 140 ( $\pm 7$  days; 84 days after Vaccination #3)**

1. Perform basic history and focused physical examination, emphasizing examination of any acute complaints.
2. Record vital signs (blood pressure, temperature, and heart rate).
3. Record AEs and concomitant medications, if applicable.

**Study Day 168 ( $\pm 7$  days; 112 days after Vaccination #3)**

1. Perform basic history and focused physical examination, emphasizing examination of any acute complaints.
2. Record vital signs (blood pressure, temperature, and heart rate).
3. Record AEs and concomitant medications, if applicable.
4. Obtain approximately 6.5 mL of blood for malaria blood smear, malaria PCR, anti-Pfs230 antibody ELISA, standard membrane feeding assay (SMFA).

**Study Day 196 ( $\pm 7$  days; 140 days after Vaccination #3)**

1. Perform basic history and focused physical examination, emphasizing examination of any acute complaints.
2. Record vital signs (blood pressure, temperature, and heart rate).
3. Record AEs and concomitant medications, if applicable.

**Study Day 224 ( $\pm 28$  days; 168 days after Vaccination #3)**

1. Perform basic history and focused physical examination, emphasizing examination of any acute complaints.
2. Record vital signs (blood pressure, temperature, and heart rate).
3. Record AEs and concomitant medications, if applicable.
4. Obtain approximately 7.5 mL of blood for malaria blood smear, malaria PCR, anti-Pfs230 antibody ELISA, standard membrane feeding assay (SMFA), and transcriptional analysis.

**Study Day 308 ( $\pm 56$  days; 252 days after Vaccination #3)**

1. Perform basic history and focused physical examination, emphasizing examination of any acute complaints.
2. Record vital signs (blood pressure, temperature, and heart rate).

3. Record AEs and concomitant medications, if applicable.
4. Obtain approximately 6.5 mL of blood for malaria blood smear, malaria PCR, anti-Pfs230 antibody ELISA, standard membrane feeding assay (SMFA).

**Study Day 392 (±56 days; 336 days after Vaccination #3)**

1. Perform basic history and focused physical examination, emphasizing examination of any acute complaints.
2. Record vital signs (blood pressure, temperature, and heart rate).
3. Record AEs and concomitant medications, if applicable.
4. Obtain approximately 6.5 mL of blood for malaria blood smear, malaria PCR, anti-Pfs230 antibody ELISA, standard membrane feeding assay (SMFA).

**Study Day 378 (±84 days; 322 days after Vaccination #3)**

1. Perform basic history and focused physical examination, emphasizing examination of any acute complaints.
2. Record vital signs (blood pressure, temperature, and heart rate).
3. Record AEs and concomitant medications, if applicable.
4. For females, obtain a urine or serum sample for  $\beta$ -hCG testing. Ensure that the test is negative before vaccinating.
5. Obtain approximately 12.5 mL of blood for CBC with differential and platelet count, ALT, creatinine, malaria blood smear, malaria PCR, anti-Pfs230 antibody ELISA and standard membrane feeding assay (SMFA) and transcriptional analysis.

**Day 392 (±112 days; day of Vaccination #4)**

The following evaluations/procedures will be completed before vaccination:

1. Perform interim history and physical examination, focusing on any acute complaints.
2. Record vital signs (blood pressure, temperature, and heart rate).
3. During the physical examination, study staff will educate the subject regarding signs and symptoms of potential adverse events (AEs) and indications for use of antipyretics if fever, headache, or malaise occurs.
4. For females, obtain a urine or serum sample for  $\beta$ -hCG testing. Ensure that the test is negative before vaccinating.
5. For females, ensure agreement and compliance with pregnancy prevention before vaccinating.
6. Obtain approximately 11.0 mL of blood for CBC with differential and platelet count, ALT, creatinine, malaria blood smear, malaria PCR, anti-Pfs230 antibody ELISA, and standard membrane feeding assay (SMFA).
7. Confirm continued eligibility to receive vaccination.
8. Administer the vaccine.

The following evaluations/procedures will be completed following vaccination:

1. Observe the subject for at least 30 minutes after vaccination to evaluate immediate adverse reactions.
2. Record vital signs (blood pressure, temperature, and heart rate).
3. Perform interim history and physical examination, focusing on any acute complaints.
4. Record AEs and concomitant medications, if applicable.

**Study Day 395 ( $\pm 1$  day; 3 day after Vaccination #4)**

1. Perform basic history and focused physical examination (including injection site), emphasizing examination of any acute complaints.
2. Record vital signs (blood pressure, temperature, and heart rate).
3. Record AEs and concomitant medications, if applicable.
4. Obtain approximately 6.0 mL of blood for CBC with differential and platelet count, ALT and transcriptional analysis.

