### **3.3.1.4 ≥19 Years Old (Main, Vaccinated)**

At the time of the fourth dose amendment (V5.0), 490 subjects aged ≥19 years old have received at least one vaccination, with 479 receiving 2 doses, and 482 receiving 3 doses.

Vaccinations were well tolerated with majority of the reported AEs being mild and majority of Grade 1 AEs reported being expected local site reactogenicity. As noted in the pediatric age groups, adults also had an increase in pyrexia reporting post dose #2, though not as frequent or severe. As seen with the younger kids, as expected, most commonly reported unsolicited AEs have been malaria and rhinitis.

Grade 3 AEs have been reported in 11 subjects (11/490, 2.2%) during the course of the study with 1 related Grade 3 AE (neutropenia) reported. One SAE, which was also a Grade 4 AE, (increased creatinine, not related to vaccination) has been reported.

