**Table 15. Solicited Adverse Events**

Systemic adverse events
Fever (temperature $\geq 38.0$ °C)
Headache
Nausea/Vomiting
Diarrhea
Abdominal pain
Fatigue
Myalgia
Arthralgia
Urticaria
Laboratory adverse events
Hemoglobin – decreased hemoglobin
WBC – leukopenia, leukocytosis
ANC/AGC – decreased neutrophil/granulocyte count
Platelet count – thrombocytopenia
ALT – increased ALT
Cr – increased Cr
Local reactogenicity
Injection pain/tenderness
Injection erythema/redness
Injection swelling
Injection induration
Injection pruritus
Limitation of arm movement

Abbreviations: ALT, alanine transaminase; ANC, absolute neutrophil count; AGC, absolute granulocyte count; CR, creatinine; WBC, white blood cell.

Additional laboratory abnormalities other than those specified as safety labs in the protocol should be reported as AEs if they require intervention. Interventions include, but are not limited to, discontinuation of treatment, dose reduction/delay, additional assessments, or concomitant treatment. In addition, any medically important laboratory abnormality may be reported as an AE at the discretion of the investigator. This could include a laboratory result for which there is no intervention, but the abnormal value suggests a disease or organ toxicity. In addition, similar to solicited AEs, all laboratory AEs as defined in [Appendix C](#), will be collected and graded through 7 days after each vaccination or until resolved.

The investigator will assess all AEs with respect to seriousness (criteria listed above), severity (intensity or grade), and causality (relationship to study agent and relationship to research) according to the following guidelines.

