## 15.10 Halting Rules for the Protocol

Halting the study requires immediate discontinuation of study agent administered for all subjects and suspension of enrollment until a decision is made whether or not to continue enrollment and study agent administration.

The following criteria will be used to define unacceptable reactogenicity of the malaria vaccine (AEs that are possibly, probably, or definitely related to the vaccine will be considered “related” and will be summarized as such); note Year 1 and Year 2 will be evaluated independently given time between dosing:

- One or more subjects experience death or any life-threatening SAE, **or**

- $\geq 2$  subjects experience an SAE as defined in **Section 15.1** of this protocol that is determined to be possibly, probably, or definitely related to the vaccine, **or**
- $\geq 1$  subjects are withdrawn from the study (by investigator or subject request) following a Grade 3 AE that is determined to be possibly, probably, or definitely related to the vaccine, **or**
- $\geq 1$  subjects experience a hypersensitivity reaction (e.g. anaphylaxis, diffuse urticaria) that is determined to be possibly, probably, or definitely related to the vaccine, **or**
- $\geq 1$  subjects experience any local or solicited AE leading to hospitalization, or fever  $>40^{\circ}\text{C}$  ( $104^{\circ}\text{F}$ ) that is possibly, probably, or definitely related to the vaccine, or necrosis at the injection site, within the 7 days post vaccination, **or**
- $\geq 10\%$  subjects enrolled experience any Grade 3 solicited local AE (lasting 48 hours or more) that is determined to be possibly, probably, or definitely related to the vaccine as defined in this protocol, within the 7 days post vaccination, **or**
- $\geq 10\%$  subjects enrolled experience any Grade 3 solicited systemic AE (lasting 48 hours or more) that is determined to be possibly, probably, or definitely related to the vaccine as defined in this protocol, within the 7 days post vaccination, **or**
- $\geq 30\%$  subjects enrolled experience the same Grade 2 or higher laboratory abnormality (see **Appendix C**) or  $\geq 10\%$  subjects enrolled experience the same Grade 3 or higher laboratory abnormality regardless of vaccine relationship, within the 7 days post vaccination, **or**

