1 Visit windows are based off timing of days post the preceding vaccination; broad visit window in place for Booster dose in attempt to group VU together and provide flexibility given the ongoing COVID pandemic 2 SMFA may be completed on subjects at Study Day 336 and 448; other SMFA time points indicated above will be completed depending on associated ELISA and DSF results at that time point. 3 DSF will be completed twice monthly post Vaccination #4 from day 406 through 532 (total = 10 feeds).																					

Year 2: Arms 3e/3f (≥19 years of age)

Arms 3e/3f (Adults 19 years of age and older)		Months	13.5	14				15	16	18	20	23	26
		Visits	24	25	26	27	28	29	30	31	32	33	34
Procedures	Blood Volume	Study Day	378 (Rescreening)	392	395	399	406	420	448	504	560	644	728
		Days post Vac	322	336/0	3	7	14	28	56	112	168	252	336
		Visit Windows (days) (1)	±84	±112	±1	±2	±7	±7	±7	±7	±28	±56	±56
Clinical Procedures													
Updated medical history/ physical													
Reconsent			X										
Pre-test/Post-test HIV counseling			X										
Interim clinical evaluation			X	X	X	X	X	X	X	X	X	X	X
AE/SAE assessment			X	X	X	X	X	X	X	X	X	X	X
Pregnancy Prevention			X	X	X	X	X	X	X	X	X	X	X
Conmed review			X	X	X	X	X	X	X	X	X	X	X
VACCINATION			X										
Unblinding											X		
Laboratory Procedures													
CBC with differential	EDTA		2	2	2		2						
ALT/ Creatinine	SST			3	3		3						
HIV testing	SST		5										
Urine/Serum pregnancy test (females only)	Urine Container or SST		0.5	X									
Malaria Blood Smear	CAP/EDTA		0.5	0.5			0.5		0.5	0.5	0.5	0.5	0.5
Malaria PCR/Genotyping/ Gametocyte	CAP/EDTA		0.5	0.5			0.5		0.5	0.5	0.5	0.5	0.5
Pfs230 ELISA	SST		5	5		5	10		5	5	5	5	5
SMFA (2)													
Transcriptional analysis	PAXGene		1		1		1				1		
Daily blood draw volume in mL			12.5	11.0	6.0	5.0	17.0	0.0	6.0	6.0	7.0	6.0	6.0
Cumulative blood volume in mL			161.0	172.0	178.0	183.0	200.0	200.0	206.0	212.0	219.0	225.0	231.0
1 Visit windows are based off timing of days post the preceding vaccination; broad visit window in place for Booster dose in attempt to group VU together and provide flexibility given the ongoing COVID pandemic													
2 SMFA may be completed on subjects at Study Day 392 and 448; other SMFA time points indicated above will be completed depending on associated ELISA results at that time point.													

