**Study Day 399 ( $\pm 2$  days; 7 day after Vaccination #4)**

1. Perform basic history and focused physical examination (including injection site), emphasizing examination of any acute complaints.
2. Record vital signs (blood pressure, temperature, and heart rate).
3. Record AEs and concomitant medications, if applicable.
4. Obtain approximately 5.0 mL of blood anti-Pfs230 antibody ELISA, and standard membrane feeding assay (SMFA).

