### Mali Laboratory AE Grading $\geq 15$ years of age

Hematology and Biochemistry Values 	Mild (Grade 1)	Moderate (Grade 2)	Severe (Grade 3)	Potentially Life Threatening (Grade 4)
Hemoglobin (Male) - gm/dL	9.5 – 10.3	8.0 – 9.4	6.5 – 7.9	< 6.5 and/or requiring transfusion
Hemoglobin (Female) gm/dL	8.0 – 9.0	7.0 – 7.9	6.0 – 6.9	< 6 and/or requiring transfusion
WBC Increase - 103/ $\mu$ L	11.5 – 15.0	15.1 – 20.0	20.1 – 25.0	> 25.0
WBC Decrease - 103/ $\mu$ L	2.5 – 3.3	1.5 – 2.4	1.0 – 1.4	< 1.0 with fever
Neutrophil/Granulocyte Decrease  - 103/ $\mu$ L	0.80 – 1.00	0.50 – 0.79	< 0.50	< 0.50 with fever
Platelets Decreased - 103/ $\mu$ L	100 – 110	70 – 99	25 – 69	< 25
Creatinine (Male) - $\mu$ mol/L	124.00 – 150.99	151.00 – 176.99	177.00 – 221.00	> 221.00 and requires dialysis
Creatinine (Female) - $\mu$ mol/L	107.00 – 132.99	133.00 – 159.99	160.00 – 215.99	> 216.00 and requires dialysis
Liver Function Tests/ALT - U/L	75.0 – 150.9	151.0 – 300.9	301.0 – 600.0	> 600.0

Abbreviations: ALT, alanine transaminase; WBC, white blood cell.

 The laboratory values provided in the tables serve as guidelines and are dependent upon institutional normal parameters. Institutional normal reference ranges should be provided to demonstrate that they are appropriate.

 The clinical signs or symptoms associated with laboratory abnormalities might result in characterization of the laboratory abnormalities as Potentially Life Threatening (Grade 4). For example, a low sodium value that falls within a grade 3 parameter should be recorded as a grade 4 hyponatremia event if the subject had a new seizure associated with the low sodium value.

 Note, neutropenias are graded and followed, but based on previous experience in African populations, should be interpreted with caution since lower values are more frequently observed in people of African descent.

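### Appendix B leaves creatinine off the adult safety draw three days after dose 4 (Arms 3e/3f, Day 395), although Appendix A schedules it

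*Combined protocol and SAP*

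**What the plan says.** Section 11 describes Appendix A as the summary of the schedule and Appendix B as the detail.

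- **Appendix B, Arms 3e/3f, Study Day 395** (3 days after Vaccination #4, ±1 day): "Obtain approximately 6.0 mL of blood for CBC with differential and platelet count, ALT and transcriptional analysis".
- **Appendix A, Year 2, Arms 3e/3f**: the row "ALT/ Creatinine" carries a 3 mL serum tube at Days 392, 395 and 406. The printed daily volume at Day 395 is 6.0 mL.
- **Table 15** includes "Cr – increased Cr" among the solicited laboratory events.
- **Section 15.3** says that laboratory events defined in Appendix C "will be collected and graded through 7 days after each vaccination or until resolved". Appendix C grades creatinine for participants aged 15 and over, and so for all adults in these arms.
- **Appendix B, Arms 3e/3f, Study Day 399** (7 days after Vaccination #4, ±2 days): "Obtain approximately 5.0 mL of blood anti-Pfs230 antibody ELISA, and standard membrane feeding assay (SMFA)". No safety laboratory test is named at that visit.

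**The concern.** Two parts of the operative schedule give different instructions for the same visit. The analyte left out is one the protocol solicits by name, and the visit is the one on which its 7-day collection after dose 4 depends. A clinic working from the detailed list, as Section 11 invites it to do, could order ALT from the tube and not order creatinine.

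What is at stake is the completeness of the adult laboratory safety record after dose 4. Because Arms 3e and 3f share one list, the gap would fall on vaccine and comparator adults alike. It would not favour either arm, but it would leave no nominally scheduled creatinine value in the window to compare.

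**Working it through.** **Step 1. Does the printed volume include the creatinine tube?** The tube volumes come from Appendix A, Year 2, Arms 3e/3f. Summing them by visit checks that the table columns have been read correctly.

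| Day | Tubes (mL) | Sum | Printed |
|---|---|---|---|
| 392 | CBC 2 + ALT/creatinine 3 + smear 0.5 + PCR 0.5 + ELISA 5 | 11.0 | 11.0 |
| 395 | CBC 2 + ALT/creatinine 3 + transcriptional 1 | 6.0 | 6.0 |
| 399 | ELISA 5 | 5.0 | 5.0 |
| 406 | CBC 2 + ALT/creatinine 3 + smear 0.5 + PCR 0.5 + ELISA 10 + transcriptional 1 | 17.0 | 17.0 |

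All four sums match. The 6.0 mL printed in Appendix B for Day 395 is therefore the volume with the shared ALT/creatinine tube included. Without that tube it would be 2 + 1 = 3.0 mL.

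**Step 2. Does another adult visit cover the 7 days after dose 4?** The visits and windows are those in Appendix B, counted in days after the dose.

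- Day 392: creatinine is listed, but among the procedures done before vaccination, so it is a baseline value.
- Day 395: 3 ±1, days 2 to 4. CBC and ALT are named; creatinine is not.
- Day 399: 7 ±2, days 5 to 9. ELISA and SMFA only.
- Day 406: 14 ±7, days 7 to 21. Creatinine is listed, but the nominal day is 14. Only a visit on the earliest permitted day would fall within 7 days.

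Nominal post-dose creatinine draws within 7 days are therefore 1 under Appendix A (Day 395) and 0 under Appendix B.

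**Step 3. Is the omission a pattern or a single instance?** Appendix B has 3 age blocks with 4 doses each, so 3 × 4 = 12 lists for the visit three days after a dose.

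- Ages 5-8: creatinine named after doses 1, 2, 3 and 4 (4 of 4).
- Ages 9-18: named after doses 1, 2, 3 and 4 (4 of 4).
- Adults: named after doses 1, 2 and 3, not after dose 4 (3 of 4).

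The total is 4 + 4 + 3 = 11 of 12. The adult lists after doses 1 to 3 also print 6.0 mL, the same volume as Day 395. No reason is given for dropping the test in adults after dose 4.

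**The case against.** The strongest reply is that the documents already show what was meant. Appendix A schedules the tube, the printed volume includes it, Table 15 solicits the event, and every parallel list names the test. A clinic that draws 6.0 mL has the sample in hand. That stands, and it is why the point is minor. It does not remove the conflict, because the instruction read at the visit still leaves out a solicited analyte.

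It is also fair to say that Section 15.3 sets a collection and grading period and not draw days. The direct contradiction is with Appendix A. Section 15.3 explains why the missed test matters.

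A reader might infer three stronger things that the documents do not support.

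- **That the halting rule is compromised.** Section 15.10 counts "subjects enrolled experience the same Grade 3 or higher laboratory abnormality regardless of vaccine relationship, within the 7 days post vaccination", but the threshold is at least 10% of subjects at Grade 3 or higher, or at least 30% with the same abnormality at Grade 2 or higher. Table 4, from the earlier adult trial, shows no creatinine increase within 7 days of doses 1 to 3 in either Pfs230 arm, and a single Grade 1 event under Engerix-B. The rule stays in force, and its CBC and ALT counts are unaffected.
- **That a renal signal in adults makes this urgent.** Section 3.3.1.4 records: "One SAE, which was also a Grade 4 AE, (increased creatinine, not related to vaccination) has been reported". That is one event, judged unrelated, reported before dose 4. It is not evidence of a vaccine effect.
- **That missing values would be reported as no events.** I found nothing in the plan saying that unmeasured laboratory values are counted as zero.

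**Conclusion.** The omission is real and the point holds as a minor drafting error. Appendix B's adult Day 395 list conflicts with Appendix A and is the only one of 12 comparable lists without creatinine. Followed as printed, it reduces the nominally scheduled adult creatinine measurements in the 7 days after dose 4 from 1 to 0. The primary analysis, sample size and power are not affected.

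This rests on nominal visit days. A Day 406 visit on its earliest permitted day, or an unscheduled test, could still give a value within the window. The documents do not state how many adults received dose 4 or whether any visit was run from the short list, so the number affected is unknown. It cannot exceed 490, the adults with at least one Year 1 vaccination (Table 7), because Year 2 admits no new participants.

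**What to change.** In Appendix B, Arms 3e/3f, Study Day 395, add creatinine after ALT so that the list matches Appendix A. The volume stays at 6.0 mL, because the 3 mL shared tube is already counted. The cost is one word, with no extra visit and no extra blood.

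If any adult Day 395 visit was run without creatinine, report that adult's creatinine after dose 4 as not assessed, and give the number assessed beside any adult creatinine result for that period.
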